Expected effect:	ENDOANGEL's intended use is to assist doctors in identifying patients who require a second colonoscopy, thus avoiding missed adenomas and excessive washing time costs due to subjective factors and poor decision-making. It can improve the quality of endoscopy and the detection rate of digestive tract lesions.
Primary Endpoint:	1. Adenoma detection rate (ADR); 2. Boston Bowel Preparation Score of intestinal segment in artificial intelligence system;
Secondary Endpoints:	1. Polyp detection rate (PDR); 2. Mean number of adenomas per procedure (MAP); 3. Mean number of polyps per procedure (MNP); 4. The detection rate of large, small and micro - small adenoma and the average number of detection; 5. The detection rate and average number of polyps in large, small and micro-sized polyps; 6. Adenoma detection rate (ADR) of different location 7. Mean number of adenomas per procedure (MAP) of different location 8. Scope-forward time; 9. withdrawal time; 10. Cecal intubation rate; 11. Boston Bowel Preparation Score of endoscopists;
Trail design:	prospective, single group, observational, single-centre
Participants:	Male and female subjects aged 18 years or older will require a colonoscopy, and voluntarily provide endoscopic imaging data and sign an informed consent form.
Sample size:	200 samples were collected to explore the sample distribution, and then calculate the sample size according to the sample distribution.
Study Process:	Subjects who met all inclusion criteria and did not meet all exclusion criteria were included in the study before colonoscopy. During the colonoscopy, the endoscopists need to remain in the same without withdrawal while flushing the bowel. The biopsied patients are followed up for one week. the non-biopsied patients are followed up at the end of their colonoscopy , and the results are sent to an independent data analysis team for review. We will collect the patients' video and exclude the clips of irrigation, biopsy, and

[figure not shown]

	observation of polyp. Then the EndoAngel evaluates the Boston Bowel Preparation Scale of the ascending colon, transverse colon and descending colon, and calculates the proportion of 1 Score.
Security	Safety incidents shall be evaluated and reported according to the quality management measures for clinical trials of medical devices

1.1. Time and Event Tables

Events	Screening period (d -30~ -1)	The day of colonoscopy (d 0)	Follow up (d 1-14)
Informed Consent	X		
Basic characteristics	X		
Medical history/surgical history	X		
Inclusion/Exclusion Criteria	X		
Colonoscopy		X	
Concomitant treatment	X	X	
Concomitant medication	X	X	
Adverse Events		X	X
Research completed			X

1.2. Flow chat

Follow-up Time: The biopsied patients are followed up for one week. the non-biopsied patients are followed up at the end of the study

2. Introduction

Colorectal disease as a common human disease seriously affects the health of human life. With the aging of the population, the change of diet structure and the aggravation of environmental pollution, the incidence of colorectal diseases, such as colon cancer, Colon Polyp and inflammatory bowel disease, has gradually increased¹⁻².

Colonoscopy is the simplest and most widely available screening procedure for colorectal cancer(CRC) prevention and early detection². Colonoscopy can clearly observe the small changes in the terminal ileum and the colorectal, such as erosion, ulcers, bleeding, congestion, edema, polyps, early cancer, and so on. Colonoscopy can biopsy the lesion site for pathological examination, to histologically qualitative the characterization of mucosal lesions, such as inflammation, polyp nature, the degree of differentiation of cancer, and so on. It is helpful to understand the severity of the lesion and guide the formulation of the correct treatment plan or judgment of treatment effect. Colonoscopy can also be the minimally invasive endoscopic treatment of colorectal polyps, early cancer, bleeding, foreign bodies and other diseases.

Because the quality of bowel preparation affects the colonoscopy's ability to detect adenomas and polyps, adequate bowel preparation is necessary to ensure optimal use of colonoscopy in CRC prevention³. Almost all clinical guidelines recommend adequate bowel preparation before colonoscopy⁴⁻⁶. However, up to one third of colonoscopies have been found to show inadequate bowel preparation, which is estimated to increase the cost of colonoscopies by 12% to 22%. And there are 20% of patients' bowel is not adequately prepared. When the patient's bowel preparation is inadequate, the difficulty of flushing may lead to missed detection of adenomas⁷⁻⁹. so doctors need to accurately identify such patients and tell them to have a second colonoscopy after a full bowel cleanse¹⁰. However, the evaluation of intestinal cleanliness is decided by doctors subjectively, and there is no objective and effective scoring standard to guide the patients to accept the second colonoscopy.

Deep learning is an important breakthrough in the field of artificial intelligence in the past decade. It has great potential in extracting tiny features in image analysis and image classification. In 2017, the journal Nature published a paper showing that using artificial intelligence to diagnose skin diseases can reach the level of experts¹¹. Subsequently, in the field of digestive endoscopy, more and more studies began to apply artificial intelligence to assist doctors to find polyps and improve the detection rate of polyps and adenomas.Urban, G. team used artificial intelligence to identify polyps with 95% sensitivity¹². Misawa, M team used artificial intelligence to identify polyps with 90% sensitivity¹³. The purpose of our research group is to develop the EndoAngel with real-time intestinal cleanliness assessment. It can derive a decision curve for bowel cleanliness based on the relationship between the percentage of bowel segments with a Boston score of 1 and the detection rate of missed adenomas. It can help endoscopists to identify patients who need a second colonoscopy, to avoid the detection of missed adenomas and the high cost of cleaning time caused by the wrong decision-making. At the same time, artificial intelligence is in

the preliminary research stage in the field of digestive endoscopy, our research results are expected to provide new ideas in improving the detection rate of colonoscopic adenomas.

2. Patient Selection

Male and female subjects aged 18 years or older will require colonoscopy. And they voluntarily provide endoscopic imaging data and sign informed consent form.

Patients not meeting the inclusion criteria or meeting exclusion criteria will not be considered for participation in the study. Patients who met all criteria and signed informed consent may be excluded from the study due to:

- Endoscopists' professional advices/medical reasons (only under very limited conditions to avoid researcher bias).
- Withdraw informed consent.

2.1. Inclusion criteria

All patients meeting the following criteria will be considered for participation in the study:

- 1) Male or female aged 18 or above;
- 2) Colonoscopy is needed to further clarify the characteristics of digestive tract diseases;
- 3) Patients able to give informed consent were eligible to participate.
- 4) Able and willing to comply with all study process.
- 5) No intestinal organic disease.

2.2. Exclusion criteria

All patients meeting the following criteria will not be considered for participation in the study:

- 1) Has participated in other clinical trials, signed informed consent and was in the follow-up period of other clinical trials.
- 2) Has participated in clinical trials of the drug and is in the elution period of the experimental drug or control drug.
- 3) Drug or alcohol abuse or psychological disorder in the last 5 years.
- 4) Patients in pregnancy or lactation.
- 5) Known polyposis syndromes.
- 6) Gastrointestinal Bleeding.
- 7) A history of inflammatory bowel disease, colorectal cancer and colorectal surgery.
- 8) A history of colorectal surgery.
- 9) Patients with a contraindication for biopsy.
- 10) Previous history of allergy to ingredient of bowel cleanser.
- 11) Patients with intestinal obstruction or perforation, toxic megacolon, Colectomy, heart failure (Grade III or IV) , severe cardiovascular disease, severe liver failure or renal insufficiency, etc. .

- 12) Patients with poor bowel preparation that are unable to reach their blindness.
- 13) Researchers believe that the patient is not suitable to participate in the trial.

2.3. Definition of enrollment

After participants signed informed consent, they were regarded as enrolled. The sign time was the enrollment time, and was recorded in CRF.

3. Endpoints

3.1. Primary Endpoint

- 1) The adenoma detection rate (ADR):

ADR was calculated by dividing the total number of patients being detected adenomas by the number of colonoscopies.

- 2) Cleanliness assessment of different intestinal segment in the artificial intelligence system
The artificial intelligence system evaluates the Boston Bowel Preparation score of the ascending colon, transverse colon and descending colon in real-time, and calculates the proportion of 1 Score

3.2. Secondary Endpoints

- 1) The polyp detection rate (PDR): PDR was calculated by dividing the total number of patients being detected polyps by the number of colonoscopies.
- 2) The mean number of polyps per patient (MNP). MNP was calculated by dividing the total number of polyps by the number of colonoscopies.
- 3) The mean number of adenomas per patient (MAP). MAP was calculated by dividing the total number of adenomas by the number of colonoscopies.
- 4) PDR of different sizes. It was calculated by dividing the number of patients with polyps that large (≥ 10 mm), small (6-9 mm) and diminutive (≤ 5 mm) by the number of patients undergoing colonoscopy.
- 5) MNP of different sizes. It was calculated by dividing the number of polyps that large (≥ 10 mm), small (6-9 mm) and diminutive (≤ 5 mm) by the number of patients undergoing colonoscopy.
- 6) ADR of different sizes. It was calculated by dividing the number of patients with adenomas that large (≥ 10 mm), small (6-9 mm) and diminutive (≤ 5 mm) by the number of patients undergoing colonoscopy.
- 7) MAP of different sizes. It was calculated by dividing the number of adenomas that large (≥ 10 mm), small (6-9 mm) and diminutive (≤ 5 mm) by the number of patients undergoing colonoscopy.

- 8) ADR of different location. It was calculated by dividing the number of patients with adenomas detected in the rectum, sigmoid colon, descending colon, transverse colon, ascending colon, ileocecal region etc. by the Total number of patients undergoing colonoscopy.
- 9) MAP of different location. It was calculated by dividing the number of adenomas detected in the rectum, sigmoid colon, descending colon, transverse colon, ascending colon, ileocecal region etc. by the Total number of patients undergoing colonoscopy.
- 10) Scope-forward time. The time is taken to go from the the rectum to the ileocecal region.
- 11) Withdrawal time. The time is taken to finish the examination from the beginning of the ileocecal region.
- 12) Cecal intubation rate. It was calculated by dividing the number of colonoscopies that get to the ileocecal region by the total number of colonoscopies.
- 13) Boston Bowel Preparation Score of endoscopists. Endoscopists evaluate the different intestinal segment according Boston Bowel Preparation Scale(BBPS)

3.3. Safety evaluation endpoints and other secondary endpoints

Adverse events shall be determined according to the definition in the code for the quality management of adverse events of medical devices. The following types of adverse events should be recorded and calculated in the hospital history and CRF. According to the CRF table, the occurrence time, starting and ending time, intervention measures and treatment results should be filled in when recording. The severity should be referred to the previous literature and CTCAE 5.0 standard.

4. Purpose and overall design

4.1. Purpose

The purpose of this study is to develope the Endoangel with real-time intestinal cleanliness assessment. It can derive a decision curve for bowel cleanliness based on the relationship between the percentage of bowel segments with a Boston score of 1 and the detection rate of missed adenomas. To assist endoscopist in identifying patients who require a second colonoscopy, thus avoiding missed adenomas and excessive washing time costs due to subjective factors and poor decision-making. It can improve the quality of endoscopy and the detection rate of digestive tract lesions.

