5.1. Summary of Study Process

- If the patient meets the inclusion criteria, the patient is invited to participate in the study and then the informed consent procedure for the clinical trial is applied.
- Assess patients' eligibility based on the inclusion/exclusion criteria.
- If the patient meets the inclusion/exclusion criteria, information prior to endoscopy will be collected.
- A colonoscopy is performed after informed consent. Any intraoperative adverse events are recorded on the CRF for submission and subsequent analysis.
- Follow-up will be performed from the postoperative to the study completion, as detailed in the time and event table.

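### The decision curve is framed around missed adenomas, but no endpoint observes a miss; reading the detection curve that way rests on assumptions the plan does not state

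*Combined protocol and SAP*

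**What the plan says.** **Aim.** Section 4.1 bases the decision curve on "the relationship between the percentage of bowel segments with a Boston score of 1 and the detection rate of missed adenomas". The Introduction repeats this and adds: "It can help endoscopists to identify patients who need a second colonoscopy, to avoid the detection of missed adenomas". The synopsis gives the device's purpose in similar terms: its "intended use is to assist doctors in identifying patients who require a second colonoscopy, thus avoiding missed adenomas". The Introduction offers a mechanism, that in a poorly prepared bowel "the difficulty of flushing may lead to missed detection of adenomas".

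**What is measured.** The time and event table (1.1) marks colonoscopy on day 0 only, and 5.1 describes one examination: "A colonoscopy is performed after informed consent". The first primary endpoint (3.1) is defined so: "ADR was calculated by dividing the total number of patients being detected adenomas by the number of colonoscopies". The lesion endpoints in 3.2, by number, size and location, likewise count detected polyps or adenomas, and the list in 6.1 matches. No miss rate is defined. The follow-up to treatment in 5.3.4, item 4, covers patients whose lesions were already seen.

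**What is analysed.** Section 7.3 posits a curve relating cleanliness score to adenoma detection, then a decision on a second examination. Section 7.4 also uses adenoma detection and the percentage of score 1. Section 7.2 lists descriptive summaries only. "Basic characteristics" and medical history are recorded at screening (1.1), but no covariate or model is named.

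**The concern.** The purpose names one quantity and the endpoints supply another. To know that an adenoma was missed one needs a second look or some other reference, and the plan provides neither. The curve in 7.3 and 7.4 can be estimated. The gap lies in the step from that curve to missed adenomas, and from there to who should return for another colonoscopy.

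A lower ADR at a higher percentage of score 1 may mean that more adenomas were overlooked, that fewer were present, or that the examinations differed in another way, such as withdrawal time or endoscopist. A cut-off read from the curve could then be reported as marking patients with missed adenomas when it partly marks something else. The error can also run the other way: if patients with dirtier bowels carry more adenomas, a real rise in misses could leave the curve flat.

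**Working it through.** **The plan's own figure.** The only number is the 200 exploratory colonoscopies in 7.4. It comes with no effect size, alpha or power, so there is nothing to reproduce.

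**Identity.** At patient level, let p be the proportion with at least one adenoma and m the proportion of those in whom none is found. Then:

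- ADR = p × (1 − m)
- missed patients = p − ADR
- excess missed, dirtier minus cleaner = (ADR_c − ADR_d) + (p_d − p_c)

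One examination per patient gives one observed rate for two unknowns. All values below are assumed and illustrate the identity only.

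**Step 1: equal prevalence.** Take ADR 32% in cleaner and 24% in dirtier bowels.

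| Prevalence in both groups | Miss rate, cleaner (1 − 0.32/p) | Miss rate, dirtier (1 − 0.24/p) | Missed per 100, cleaner vs dirtier |
|---|---|---|---|
| 40% | 20% | 40% | 8 vs 16 |
| 50% | 36% | 52% | 18 vs 26 |
| 60% | 47% | 60% | 28 vs 36 |

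Relative sensitivity (0.24/0.32 = 0.75) and the excess of 8 missed patients per 100 are fixed. The level of the miss rate is not, and a larger sample does not supply it.

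**Step 2: unequal prevalence.** Hold the cleaner group at prevalence 40% and miss rate 20%, so ADR = 0.40 × 0.80 = 32% and 8 per 100 are missed.

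| Dirtier: prevalence | Dirtier: miss rate | Dirtier: ADR | Missed per 100 | What the ADR curve shows |
|---|---|---|---|---|
| 40% | 40% | 24% | 16 | falls; miss rate has doubled |
| 30% | 20% | 24% | 6 | same fall; miss rate unchanged |
| 53.3% | 40% | 32% | 21.3 | flat; miss rate has doubled |
| 60% | 40% | 36% | 24 | rises; miss rate has doubled |

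The first two rows give identical data and opposite readings. The last two show a real difference hidden or reversed. By the third formula, each point of prevalence difference moves the excess by one patient per 100.

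**Step 3: cause.** Even with comparable prevalence, the gradient shows that misses vary with cleanliness, not that cleanliness causes them. Withdrawal time is recorded (3.2, item 11) but enters no planned analysis.

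**Step 4: range of the curve.** Exclusion criterion 12 (2.2) removes some poorly prepared patients, 5.4.2 lists poor cleanliness as a reason for withdrawal during the procedure, and 7.5 makes the per-protocol set the main analysis. The dirtiest bowels may therefore be thinly represented, although the second-colonoscopy decision bears most on them.

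**Step 5: room for adjustment.** With an assumed ADR of 20% to 30%, 200 colonoscopies give 200 × 0.20 = 40 to 200 × 0.30 = 60 patients with an adenoma. At 10 events per parameter (an assumed rule of thumb), that supports about 4 to 6 parameters.

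**The case against.** This is an exploratory, single-group development study. Its endpoints, main hypothesis and sample-size text consistently use adenoma detection, and that curve is coherent. The sentence in 4.1 describes what the device can do rather than a planned analysis. The phrasing may also owe something to translation: the Introduction speaks both of avoiding the detection of missed adenomas and of missed detection. All this stands as a reason for moderate severity, though the translation reading cannot be proven. It does not remove the gap, because 7.3 itself carries the curve through to a decision about a second colonoscopy.

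Four stronger readings are tempting, and the documents do not support them.

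- A reader might infer that the whole analysis fails unless prevalence is equal at every cleanliness level. Equality conditional on measured covariates would be enough for a relative reading.
- A reader might infer that stating equal prevalence settles the matter. It does not: the level of the miss rate stays unknown and other causes of misses remain.
- A reader might infer that no patient undergoes a later procedure. Section 5.3.4, item 4, implies one for some patients with lesions already seen; it is not a second look and feeds no endpoint.
- A reader might take the illustrations as an estimate of bias. The documents give no ADR, prevalence or miss rate from which to make one.

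It is also fair to object that the recorded baseline fields are not listed and the CRF is not among the documents, so it cannot be confirmed that adenoma risk factors are collected.

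**Conclusion.** The point holds as a should-fix. The stated basis of the decision curve, missed adenomas, is observed by no endpoint, and the detection curve that replaces it supports a statement about relative misses only under assumptions the plan does not make explicit: comparable adenoma prevalence across cleanliness levels, at least given covariates, and no other explanation of the gradient such as withdrawal time or endoscopist. The absolute miss rate stays out of reach either way. The direction of any bias cannot be known in advance, and its size cannot be derived from the documents.

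A reader might go further and call this a fatal flaw. The documents do not support that: the association between the percentage of score 1 and adenoma detection can be estimated as planned, and the remedy lies in the claim and the analysis text.

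**What to change.** 1. **Synopsis, Introduction and 4.1.** Restate the aim as estimating the association between AI-scored cleanliness (percentage of score 1) and adenoma detection at the index colonoscopy.
2. **Section 7.3.** Keep the correlation-curve hypothesis. Label any second-colonoscopy cut-off as hypothesis-generating, state the assumptions given in the verdict, and say that the study will draw no conclusion on miss rates.
3. **Section 7.2.** Add a model of adenoma detected (yes/no) on the percentage of score 1, adjusted for a short pre-specified list of baseline adenoma risk factors already on the CRF, after checking that they are there. Report it beside the unadjusted curve, and add withdrawal time as a sensitivity analysis.
4. **Sections 7.3 and 7.5.** State that the curve applies only to the range of cleanliness analysed, given the exclusion and withdrawal of some poorly prepared patients and the per-protocol main analysis.

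The cost is a wording amendment, a more modest claim and one further model. If the CRF already holds the risk factors, no new data are needed. Adjustment will be partial, since unmeasured differences in prevalence remain.

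As a separate, minor item, reconcile the randomisation wording in 5.4, 6.4 and 6.6, and the control group in 6.6, with the single-group design in 4.2. Also reconcile the three definitions of enrolment: at consent (2.3), after screening (5.2.2) and after randomisation (5.4).

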4.2. Overall design

This is a prospective, single group, observational, single-centel study.

5. Study process

5.1. Summary of Study Process

- If the patient meets the inclusion criteria, the patient is invited to participate in the study and then the informed consent procedure for the clinical trial is applied.
- Assess patients' eligibility based on the inclusion/exclusion criteria.
- If the patient meets the inclusion/exclusion criteria, information prior to endoscopy will be collected.
- A colonoscopy is performed after informed consent. Any intraoperative adverse events are recorded on the CRF for submission and subsequent analysis.
- Follow-up will be performed from the postoperative to the study completion, as detailed in the time and event table.

5.2. Enrollment

Only after patients signed the informed consent, can the research-related procedures be conducted.

5.2.1. Informed Consent

According to the Helsinki Declaration, patients are not allowed to participate in the study without adequate informed consent. The principal investigator is responsible for ensuring that no patient was enrolled in the study without adequate informed consent. Failure to obtain informed consent and failure to document this process is considered a violation of the Helsinki Declaration and the study protocol.

All informed consent documents (ICDs) must be approved by ethics. Patient's informed consent requires documentary record on the informed consent by himself in his primary language.

The investigator or trained designated person performs a preliminary screening to determine if the patient generally meets the eligibility criteria for the study. If yes, the investigator or trained designee should recommend the patient to participate in the study. If the patient agrees to participate, they will need to sign an informed consent document.

The investigator or trained designated person should confirm that the subject understands the following points in the study:

- the purpose of research,
- potential risks or adverse events,
- Potential risks or adverse events directly related to participating the research,
- The likelihood of failure,
- Research requirements include follow-up visits,

- All rights of the subject as a participant in the clinical study.

After explaining the purpose of the study, the investigator or trained designee should answer any questions from the subject. If the subject agrees to participate, his or her wishes must be recorded by signing and dated on the EC-approved ICF, and the document should be signed and dated by the patient receiving the informed consent.

After successful completion of the informed consent process, the investigator or trained designated person will assess the eligibility of patients based on the protocol.

